findings have justified further evaluation of this vaccine in a randomized phase II clinical trial, a study currently underway (NCT01341652). Finally, further preliminary studies have suggested that patients previously treated with pTVG-HP have circulating PAP-specific CD8+ T cells with PD-1 expression and circulating EpCam+ circulating epithelial cells (CEC) with PD-L1 expression, analogous to our findings in murine models. These findings suggest that the pTVG-HP vaccine might specifically be used to elicit CD8+ T cells specific for prostate tumors, the efficacy of which could be augmented with concurrent treatment with PD-1 blockade. Collectively, these findings form the rationale for the current trial.

2. Background and Rationale

A. PAP is a tumor antigen in prostate cancer and PAP-specific CD8+ CTL can lyse prostate cancer cells

PAP was first identified in 1938 and was initially used as a serum marker for the detection of prostate cancer [22, 32]. PAP expression in normal and malignant prostate cells is well-documented, and is still used in immunohistochemical staining to establish a prostate origin of metastatic carcinoma [33]. The ubiquitous expression of PAP in prostate tissue makes it an appealing antigen as a potential “universal” target for immune-directed therapies of prostate cancer, unlike specific oncogenes that may or may not be expressed by a particular tumor. Moreover, it has been demonstrated that some patients with prostate cancer have preexisting antibody and T-cell responses to PAP, suggesting that tolerance to this “self” protein can be circumvented *in vivo* [34, 35]. In particular, the demonstration of Th1-like immune responses specific for PAP suggest that an immune environment permissive of an anti-tumor response can exist in patients even without immunization [36]. Moreover, we have previously demonstrated that CD8+ T cells specific for PAP, with cytolytic activity for prostate cancer cells, can exist in patients with prostate cancer, and can be augmented with vaccination [30, 36].

B. PD-1 blockade

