2. To determine the 6-month progression-free survival and median time to radiographic progression in patients with castration-resistant metastatic prostate cancer treated with pembrolizumab in combination with pTVG-HP
3. To evaluate the anti-tumor response rates (objective response rate and PSA response rate, using PCWG2 criteria) in patients with castration-resistant metastatic prostate cancer treated with pembrolizumab in combination with pTVG-HP

B. Secondary Objectives:

1. To determine whether either treatment sequence, or PAP-specific immune response, is associated with prolonged (6-month) radiographic progression-free survival
2. To evaluate effects of schedule (concurrent versus delayed administration of pembrolizumab) on the magnitude of PAP-specific T-cell responses, PD-1 expression on circulating T cells, and PD-L1 expression on circulating epithelial cells (CEC) and on tumor biopsies
3. To determine the median time to radiographic progression using concurrent administration schedules

C. Laboratory and Exploratory Objectives:

1. To evaluate effects of treatment on number of circulating tumor cells
2. To evaluate PAP-specific antibody responses following treatment with pembrolizumab and pTVG-HP DNA vaccine
3. To determine whether either treatment sequence elicits immunologic antigen spread to other prostate-associated antigens
4. To determine whether pre-existing or vaccine-induced PD-L1 expression on CEC or tumor biopsies is predictive of objective clinical response
5. To determine whether treatment elicits expression of other regulatory molecules on tumor-specific T cells (e.g. TIM3, BTLA, and LAG3) or tumor cells (e.g. HVEM, phosphatidyl serine, PD-L2)
6. To determine whether PD-1-regulated antigen-specific T cells identified by *trans vivo* DTH testing can identify patients who develop objective clinical responses with PD-1 blockade therapy in combination with pTVG-HP
7. To determine whether changes in lymph nodes and soft tissue tumor lesions are observed by FLT PET/CT after treatment with vaccine with or without pembrolizumab
8. To determine if PD-1 inhibitor therapy in combination with pTVG-HP will change number and activity (SUV) in osteoblastic metastases as measured by NaF PET/CT.

4. Product Information

A. Anti-PD-1 monoclonal antibody (Pembrolizumab, Keytruda®)

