15. Any other medical intervention or condition, which, in the opinion of the PI or treating physician, could compromise patient safety or adherence with the study requirements (including biopsies or leukapheresis procedures) over the primary 3-6 month treatment period.
16. Patients cannot have concurrent enrollment on other phase I, II, or III investigational treatment studies.

17. NOTE: There is no exclusion for prior immune-based therapy. This includes patients previously treated on Arms 1 or 2 who are otherwise eligible for treatment on Arm 3 or 4.

6. Experimental Design

This will be a 1:1 randomized, open-label, single institution pilot trial designed to evaluate the immunological and clinical effect of a DNA vaccine encoding PAP with rhGM-CSF adjuvant given with (concurrently or sequentially) pembrolizumab. Study arms will be defined as follows:

Arm 1: pTVG-HP (100 µg) with rhGM-CSF (208 µg) administered intradermally (i.d.) biweekly 6 times
Pembrolizumab 2 mg/kg, administered intravenously every 3 weeks 4 times, beginning on day 1 after the first pTVG-HP vaccination

Arm 2: pTVG-HP (100 µg) with rhGM-CSF (208 µg) administered intradermally (i.d.) biweekly 6 times
Pembrolizumab 2 mg/kg, administered intravenously every 3 weeks 4 times, the first dose administered two weeks after the last pTVG-HP vaccination

Extended treatment Arm 3:

pTVG-HP (100 µg) with rhGM-CSF (208 µg) administered intradermally (i.d.) every 3 weeks, for a maximum of 16 doses
Pembrolizumab 2 mg/kg, with a maximum dose of 200 mg, administered intravenously every 3 weeks, for a maximum of 16 doses, beginning on day 1 after the first pTVG-HP vaccination

Extended treatment Arm 4:

pTVG-HP (100 µg) with rhGM-CSF (208 µg) administered intradermally (i.d.) every 2 weeks, for a maximum of 24 doses
Pembrolizumab 2 mg/kg, with a maximum dose of 200 mg, administered intravenously every 4 weeks, for a maximum of 12 doses, beginning on day 1 after the first pTVG-HP vaccination

A. Study Arm Assignment and Toxicity Assessment

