REPORTING AND RESPONSE DEFINITION: Data will be reported as a mean and standard deviation of antigen-specific (PAP-specific) CD4⁺ or CD8⁺ T cells expressing one or more cytokines per 10⁶ PBMC using triplicate assessments for each antigen-stimulation condition, as previously reported [31]. Comparison of experimental wells with control, no antigen, wells will be performed using a two-tailed Student's t test, with $p < 0.05$ defined as a significant antigen-specific T-cell response. A significant antigen-specific response resulting from immunization will then be defined as a PAP-specific response detectable at the 6-month post-treatment time point (or other post-treatment time point evaluated) that is significantly higher than to media only (as above), at least 3-fold higher than the mean baseline value, and with a frequency > 100 per 10⁶ CD4⁺ or CD8⁺ T cells.

B.4. Assessment of antigen-specific antibody immunity

Enzyme-linked immunosorbent assay (ELISA) for the detection of antibodies responses to PAP: The presence of a coexisting humoral immune response to PAP (or other antigens) will be evaluated by ELISA using an indirect method similar to that described previously [34]. Specifically, Immulon-4 ELISA plates (Dynerx Technologies Inc.) will be coated with 2 µg/ml purified PAP protein (Research Diagnostics, Inc., or other antigens or commercial sources) in 0.1 M NaHCO₃/Na₂CO₃ buffer (pH 9.6) overnight at 4°C. After blocking with PBS/1% BSA for 1 hour at room temperature, wells will be washed with PBS + 0.05% Tween-20 (PBS-Tween) and then incubated for 1 hour with human sera diluted 1:25, 1:50, 1:100 and 1:200. After washing, plates will then be sequentially incubated with a peroxidase-conjugated anti-human IgG detection antibody (Amersham), followed by peroxidase enzyme TMB substrate (Kierkegaard and Perry Laboratories). The color reaction will be stopped with 1N H₂SO₄ and the optical density measured at 450 nm. Antibody titers for PAP-specific IgG antibodies will be determined as previously described [34].

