REPORTING AND RESPONSE DEFINITION: These are not strictly quantitative assays. IgG response will be reported graphically demonstrating sera dilution curves, and by titer – defined as the highest sera dilution at which IgG responses are detectable above the mean + 3 standard deviations of the negative control. A positive IgG response resulting from immunization will be defined as an antigen-specific (anti-PAP) IgG titer at least 4-fold higher than the baseline titer detectable at the 6-month post-treatment time point (or other post-treatment time point evaluated).

B.5. Assessment of antigen-specific regulatory immune responses

Trans-vivo delayed-type hypersensitivity (tvDTH) evaluation: 7.5-10 x 10⁶ PBMC obtained from patients prior to and after immunization will be co-injected into the footpads of 6-to-8-week old SCID mice with 1 µg of PAP protein (Fitzgerald Industries, Acton, MA), or tetanus toxoid (TT/D; Aventis Pasteur, Bridgewater, NJ) as a recall antigen, versus phosphate-buffered saline (PBS) alone as a negative control. Other antigens may be evaluated as well. Antigen-driven swelling will be determined as previously described [66]. DTH reactivity after 24 hours will be shown as the change in footpad thickness in multiples of 10⁻⁴ inches, measured using a dial thickness gauge (Mitutoyo, Japan), and net swelling will be defined as the antigen-specific swelling subtracted for

the contribution obtained with PBMC plus PBS. To determine the effect of neutralizing antibodies, PBMC will be mixed with 1 µg of PAP antigen and 25 µg of either control IgG or rabbit anti-human TGF-β, goat anti-human IL-10 (R&D Systems, Minneapolis, MN), 1 µg of mouse anti-human CTLA-4 monoclonal Ab (clone AS32, Ab Solutions, Mountain View, CA), or 1 µg of mouse anti-human PD-1 monoclonal Ab (or potentially other antibodies to other regulatory molecules), and injected into the footpads of SCID mice as above. The extent of bystander suppression, defining an antigen-specific regulatory response, will be measured as inhibition of recall antigen (tetanus) response in the presence of PAP antigen (or prostate-specific antigen (PSA) as a negative control) and calculated as previously described [67]. Given the nature of the testing and the requirement for SCID mice, data will be shown derived from single measurements, but with key experiments repeated 2-3 times for confirmation.

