The number of circulating tumor cells will be summarized in terms of means and standard deviations. Within each arm, and for both arms combined, changes in the number of circulating tumor cells from the pre-treatment (date of screening/randomization) to the post-treatment assessments (day 43, day 85, day 169, month 9, and off-study) assessments will be evaluated using a paired t-test. A two-sample t-test will be used to compare the number of circulating tumor cells at each time point, and the changes in the number of circulating tumor cells from the pre-treatment assessment, between study arms. In order to evaluate longitudinal changes in the number of circulating tumor cells, linear mixed effects modeling with subject specific random effects will be conducted.

F.6.2. Evaluating of Treatment Effects on PAP-specific Antibody Responses

The number and frequency of PAP-specific antibody responses will be summarized in tabular format, stratified by study arm and for both arms combined. A generalized linear mixed effects model with subject specific random effects will be used to evaluate the treatment effect of the proposed pTVG-HP DNA vaccine and pembrolizumab (sequentially versus concurrently) combination on PAP-specific antibody response.

F.6.3. Evaluation whether Treatment with either Sequence Elicits Immunologic Antigen Spread to other Prostate Associated Antigens

The detection of antigen spread to other prostate associated antigens, and the identification of specific antigens recognized, will be analyzed descriptively. Furthermore, linear regression analysis will be conducted to evaluate whether treatment with either sequence (pembrolizumab administered sequentially or concurrently) elicits immunologic antigen spread to other prostate associated antigens.

F.6.4. Evaluation of Pre-Existing or Vaccine Induced PD-L1 Expression on CEC or Tumor Biopsies as a Predictor for Clinical Response

Logistic regression analysis will be conducted to examine whether pre-existing or vaccine induced PD-L1 expression on CEC or tumor biopsies predict clinical response. This analysis will be conducted for both arms combined. The results will be summarized in terms of odds ratios along with the corresponding 95% confidence intervals.

F.6.5. Evaluation whether Treatment with either Sequence Elicits other Regulatory Molecules on Tumor-Specific T cells or Tumor Cells

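### With sera diluted only to 1:200, a patient whose baseline anti-PAP titer is 1:100 or 1:200 cannot meet the 4-fold rule for a positive IgG response

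*Combined protocol and SAP*

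**What the plan says.** Section 10.B.4 describes an indirect ELISA for PAP-specific IgG. Coated wells are to be "incubated for 1 hour with human sera diluted 1:25, 1:50, 1:100 and 1:200". The reporting paragraph of the same section gives the titer as "defined as the highest sera dilution at which IgG responses are detectable above the mean + 3 standard deviations of the negative control". A positive response resulting from immunization is then an anti-PAP "IgG titer at least 4-fold higher than the baseline titer", at 6 months or at another post-treatment time point.

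Two other places bear on baseline titers. Section 2.A reports that "some patients with prostate cancer have preexisting antibody and T-cell responses to PAP". Section 5.B, item 17, says "There is no exclusion for prior immune-based therapy" and expressly lets patients treated on Arms 1 or 2 enter Arm 3 or Arm 4 if otherwise eligible.

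The endpoint serves the second laboratory and exploratory objective in section 3.C: "To evaluate PAP-specific antibody responses following treatment with pembrolizumab and pTVG-HP DNA vaccine". Section 11.F.6.2 says how it is used: "The number and frequency of PAP-specific antibody responses will be summarized in tabular format", by arm and for both arms combined, followed by a generalized linear mixed effects model comparing sequential with concurrent pembrolizumab.

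**The concern.** A fold-rise criterion works only if the assay can register the required rise from every baseline it can record. Here the recorded titer is capped at the top dilution, while the criterion scales with the baseline. Above some baseline the two rules are incompatible, and the patient's classification is fixed before treatment starts.

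The error runs one way. The ceiling can turn a true responder into a recorded non-responder, but not the reverse. Patients who already have PAP antibody are the ones exposed, so boosting of an existing response is what the binary endpoint would miss. Neither the tabulation nor the model in section 11.F.6.2 can recover a response that the assay had no means of recording.

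**Working it through.** **Inputs, all from section 10.B.4.** Dilutions tested: 1:25, 1:50, 1:100 and 1:200. Titer: highest detectable dilution, so at most 1:200. Threshold: post-treatment titer divided by baseline titer of at least 4. The plan states no figure of its own to reproduce.

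**Check.** Write the baseline titer as 1:b. The titer needed is 1:(4 × b), and the largest fold rise that can be recorded is 200 / b.

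| Baseline | Titer needed | Largest recordable rise | Response attainable? |
|---|---|---|---|
| 1:25 | 4 × 25 = 100, so 1:100 | 200 / 25 = 8-fold | Yes, at 1:100 or 1:200 |
| 1:50 | 4 × 50 = 200, so 1:200 | 200 / 50 = 4-fold | Yes, at the top dilution only |
| 1:100 | 4 × 100 = 400, so 1:400 | 200 / 100 = 2-fold | No |
| 1:200 | 4 × 200 = 800, so 1:800 | 200 / 200 = 1-fold | No |

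A baseline recorded as 1:200 is also censored, because the true titer may be higher. Using other post-treatment time points does not help, since the same ceiling applies at each visit.

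**Effect of extending the series.** A top dilution of 1:400 makes a response attainable from 1:100 (400 / 100 = 4) but not from 1:200 (400 / 200 = 2). A top dilution of 1:800 makes it attainable from every baseline in the present range (800 / 200 = 4). In general the top dilution must be at least 4 times the baseline titer.

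**Size.** Let q be the proportion of patients with baseline 1:100 or above, and r the proportion of those who would truly show a 4-fold rise. The recorded response rate falls short of the true one by q × r. This lies between 0 and q. The documents give neither q nor r, so no value can be computed. As a scale, one misclassified patient lowers the rate by 1/16 = 6.25 percentage points with the 16 patients planned in each of Arms 1 and 2, and by 1/20 = 5 points with the 20 planned in each of Arms 3 and 4.

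**Adjacent gap.** A patient negative at 1:25 has no defined baseline titer, so the ratio is undefined without a rule. If 1:12.5 were assigned, 1:50 would be needed; if 1:25 were assigned, 1:100 would be needed. Both are attainable, so this gap does not create the same impossibility.

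**The case against.** The strongest reply is that section 10.B.4 defers to a cited publication for how titers are determined and calls the assay similar to that method. If that method titrates positive sera to endpoint, the laboratory may already go beyond 1:200. The publication cannot be checked here. What stands is that the conclusion holds for the rule as written: the section names four dilutions and says nothing of going further. It is therefore too strong to infer that such a patient could never respond in practice. If the laboratory does titrate further, a sentence saying so settles the matter.

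Second, the section says these assays are not strictly quantitative and also calls for dilution curves to be shown graphically. A shift in a high-baseline patient might be visible there. That mitigates the problem in part, but the binary call, which is what gets counted and modeled, would still miss it.

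Third, the endpoint is exploratory and drives no sample size or primary test. That is correct, and it limits how much the point matters.

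**Conclusion.** The point holds as a minor one. Under the stated dilutions, titer definition and 4-fold rule, baselines of 1:100 and 1:200 cannot lead to a positive call. Any resulting bias in the exploratory antibody response rate is downward and of unknown size.

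Three stronger readings are tempting, and the documents do not support them:

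- **That high baselines are to be expected.** Section 2.A says only that some patients have PAP antibody, without frequency or titer, and detectable at 1:25 is not 1:100 or above. For the earlier trials of this vaccine, sections 1 and 2.D report T-cell responses, not antibody titers. High baselines are possible; no more can be said.
- **That the loss can be quantified.** Suppose a true response rate of 40% and 10% to 30% of patients at 1:100 or above. The recorded rate would be 0.40 × 0.90 = 36% down to 0.40 × 0.70 = 28%. Both inputs would be invented, and the formula also assumes that high-baseline patients respond as often as the rest. Likewise, two of four titer categories being affected says nothing about the share of patients.
- **That the planned arm comparison is biased.** The model in section 11.F.6.2 contrasts sequential with concurrent dosing and refers to both arms, which reads naturally as the randomized Arms 1 and 2. Patients re-enrolled from those arms can enter only Arms 3 and 4, and other prior immune therapy is balanced in expectation by randomization. The re-enrolment route can therefore affect only the descriptive rates in Arms 3 and 4.

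**What to change.** In section 10.B.4, require that whenever the baseline serum is positive at 1:100 or above, the paired baseline and post-treatment sera are titrated to endpoint, to at least 4 times the baseline titer. For a baseline of 1:200 that means at least 1:800. Titration to endpoint is better than a new fixed top dilution, which would only move the ceiling. If the cited method already provides this, say so in the section.

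If further titration cannot be done, do not drop these patients from the main denominator, because section 11.F.2 makes the ITT population primary for correlative outcomes. Keep the ITT rate as primary, report how many patients have a baseline of 1:100 or above, and add a sensitivity rate among patients whose baseline allows a 4-fold rise. The detailed SAP promised in section 11.F.1 is the natural place for this.

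The cost is a few extra ELISA wells for the patients concerned. Section 10.B has sera stored in aliquots at -80°C, so no new collection is needed while aliquots remain.

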The following section describes the schedule for prescreening, treatment, and clinical and laboratory evaluations. When a chemistry panel is indicated the following tests are performed: Chem 7 (including sodium, potassium, bicarbonate, BUN, creatinine, and glucose), ALT, AST, bilirubin, alkaline phosphatase, amylase, thyroid stimulating hormone (TSH) and LDH. Whenever a CBC is indicated, this will include differential and platelet count. This plan is summarized in the Schema.

Because one biomarker endpoint is to evaluate metastatic tissue prior to and after treatment, patients with disease amenable to biopsy will initially be required to undergo one pretreatment biopsy and one post-treatment biopsy roughly three months after the start of treatment. It is our intent to have at least 6 patients per study arm with evaluable pre-treatment and post-treatment

biopsies. If this is reached, subsequent patients with viable lesions amenable to biopsy may not be required to undergo these procedures. It is expected that some patients may have a baseline biopsy and not be able to undergo a repeat biopsy, and some patients may not have viable disease to biopsy, and these instances will not affect study participation. Similarly, up to 6 subjects per arm will be required to complete the FLT PET scan at baseline and again at month 3 (Week 12). If there are subjects who complete the first but not the second scan, more than 6 subjects in an arm may, after approval from the Study PI, undergo the FLT PET scans in order to have at least 6 subjects who complete both scans. A maximum of 10 evaluable subjects between Arms 3 and 4 will be required to undergo the NaF PET scans. Selected subjects in Arm #3 will undergo either the FLT PET or the NaF PET based on the area of their disease (soft tissue vs bone). Subjects in Arm 4 will not receive additional biopsies but may undergo NaF PET.

FIRST COHORT: STUDY ARMS 1 and 2:

A. Prescreen / Eligibility (performed within 6 weeks of Day 1)

1. Confirm potential eligibility by history, pathology, diagnosis; no exclusions by history
2. CT scan of abdomen and pelvis, bone scan
3. Sign consent form
4. Evaluation of CBC, chemistry panel, serum prostate specific antigen (PSA), serum PAP, and serum testosterone.

B. Pre-Treatment Evaluations (within 4 weeks of Day 1; can coincide with prescreen evaluation)

1. Physical examination, symptoms assessment, and ECOG performance score
2. Randomization – treatment arm assignment

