REPORTING AND RESPONSE DEFINITION: A positive IgG response will be defined as an immunoreactive spot to a defined antigen, scored by at least 3 of 4 independent reviewers, and detectable to at least 2 of 3 replicates per immunoblot membrane as previously described [68, 77], or by statistically defined criteria using commercial antigen sources. An IgG response resulting from immunization will be defined as an immunoreactive antigen identified at the 6-month (or other post-treatment time for subsequent analyses) time point that was not identified at the pre-treatment time point.

C. Circulating Tumor Cell (CTC) Evaluation

CTC will be enumerated and characterized at the same time points as for immune evaluation (pre-treatment, after 6 weeks, and at quarterly intervals for up to one year) using flow cytometry. Specifically, as in Figure 7, PBMC obtained at these time points will be stained with fluorochrome-labeled antibodies specific for, and including at least, CD45, EpCAM, PD-1, CTLA-4, and DAPI. CTC will be defined as CD45-EpCAM+DAPI- cells, and the percentage of these events among all live cellular events will be determined at the different time points. The % of CTC expressing PD-1 or CTLA-4 will also be determined. Results will be reported in tabular format from the different time points, and general trends will be assessed. These results will not be strictly quantitative, as multiple replicates to determine standard deviation are not feasible. Other methods of CTC capture and enumeration may also be used. Further investigational studies may be conducted with CTC collected by these methods.

D. Histopathology Evaluation

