Tissue biopsies will be obtained from metastatic lesions (the same lesion per patient) prior to treatment and at week 12. The purpose of these studies is to determine whether immunization affects PD-L1 expression in the tumor (likely by eliciting tumor antigen-specific T cells secreting IFN γ), whether concurrent treatment with anti-PD-1 mAb leads to an increase in infiltration of CD8+ T cells, and whether treatment increases expression of other T-cell regulatory ligands on T cells (PD-1, CTLA-4, TIM-3, BTLA, LAG-3) or tumors (e.g. HVEM, phosphatidyl serine, PD-L2). Consequently, biopsy specimens obtained pre-treatment and after 12 weeks will be stained with antibodies specific for CD3, CD4, CD8, FoxP3, PD-1, CTLA-4, TIM3, BTLA, LAG-3, PD-L1, PD-L2, phosphatidyl serine, HVEM and potentially other markers. Staining and quantification will be reviewed by a pathologist blinded to the treatment groups to determine CD8+ T cells per field, CD4+FoxP3+ (Treg):CD8+ T cell ratio, PD-L1 expression, and whether these or the expression of CD8+ T cells expressing one regulatory receptors (or tumor cells expressing one or more regulatory ligands) change from pre-treatment to the 12 week time point.

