3'-Deoxy-3'-[¹⁸F]Fluorothymidine (FLT) positron emission tomography (PET)/computed tomography (CT) uses a thymidine analogue that accumulates in proliferating tissue. Proliferating tissue could include malignant lesions or immune cells. Following vaccination we have observed a proliferation of CD4+ and CD8+ T cells specific for PAP, at least as assessed *in vitro* following reencounter with the PAP antigen [29, 31]. In a study of patients with melanoma treated intranodally with a dendritic cell vaccine, FLT PET/CT could detect uptake in treated lymph nodes compared to control lymph nodes following vaccination, uptake that persisted for up to 3 weeks [78]. Consequently, FLT PET/CT may be useful as a molecular imaging tool to detect immune activation after immunization, at the same time as detecting decreases in proliferating tumor masses as a result of treatment. We hypothesize that FLT PET/CT will be able to detect increased uptake in left axillary draining lymph nodes (draining site of intradermal immunization) at 12 weeks compared with pre-treatment studies, and that a decrease in uptake will be observed in soft tissue metastatic deposits. FLT PET/CT will be performed at baseline (within 4 weeks of starting treatment) and at week 12, thus enabling comparative evaluation with other imaging obtained at that time and biopsy results.

FLT PET/CT IMAGING PROCEDURES: To ensure uniformity as well as optimal data interpretation, analyses will be conducted under the supervision of [name], PhD (co-investigator) at the University of Wisconsin Image Analysis Core (IMAC) facility, with all radiographic analysis by [name] and designees blinded to study treatment arm.

- At the beginning of each imaging session, a CT scan will be obtained on the combined PET/CT scanner. The CT scan is an integral part of the PET/CT acquisition and serves for attenuation correction calculations and better PET/CT image co-registration. It will enable better delineation of the patient anatomy, which will be important when comparing different scans. An FLT-PET scan will follow. The patients will be injected up to 15 mCi (555 MBq) of ¹⁸F-FLT.

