All specimens obtained for the immunological evaluation of this trial (blood specimens) will be delivered to the laboratory of [name]. Specimens received by [name] lab will only be handled by laboratory personnel who have undergone HIPAA training and annual UWHC-mandated blood-borne pathogen safety training. Receipt of specimens will be entered into a database that will provide a unique code for each specimen. All stored specimens (sera, peripheral blood mononuclear cells) will be labeled with this unique code and the date of preparation. Thus, all patient identifiers will be removed from the final stored samples, and any data generated will contain only the unique code as identifier. A database will be maintained to link individual coded specimens with an individual subject (name, hospital medical record number, date/time point) in

order to be able to compare information from samples obtained at different time points from a specific individual, and ultimately for transfer of research data to the clinical trials database, if necessary. This research database will only be available to the study investigators, not other laboratory personnel, to maintain confidentiality. Subject sera will be maintained in [name] laboratory, stored in aliquots at -20°C to -80°C . Peripheral blood mononuclear cells will be stored in [name] laboratory, stored in aliquots in liquid nitrogen. If warranted, samples may be sent to an external institution or a contract research organization for the purpose of collaboration and /or analysis.

Subjects will have the option to consent to future research using both their samples and data which may be used independently. Samples remaining after the primary analysis has been completed and available for future research will be "banked" and stored as they were for this study unless they are selected to be sent for research elsewhere, which may be within or outside of the University of Wisconsin. Subjects wishing to withdraw their banked samples will be required to provide written notice to the principal investigator, otherwise their samples may be used indefinitely for cancer research. All research samples and data derived from these specimens will be maintained indefinitely in the laboratory of [name]. All information with patient identifiers or medical history information will be kept in locked cabinets or secured databases available only to the study personnel to maintain patient confidentiality.

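### Section 10.D masks the biopsy reader to treatment group but makes no provision for masking time point, although the reader must judge change from pre-treatment to week 12

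*Combined protocol and SAP*

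**What the plan says.** Under Section 10.D, the same metastatic lesion is biopsied "prior to treatment and at week 12". The stated masking is: "Staining and quantification will be reviewed by a pathologist blinded to the treatment groups". That pathologist is to determine CD8+ cells per field, the Treg:CD8 ratio, PD-L1 expression and regulatory receptors and ligands, and whether these "change from pre-treatment to the 12 week time point". Some of the questions have a direction, for example "whether concurrent treatment with anti-PD-1 mAb leads to an increase in infiltration of CD8+ T cells". Neither 10.D nor the statistical section (Section 11) mentions masking of time point, random reading order, a second reader or automated scoring.

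Section 9 aims for "at least 6 patients per study arm with evaluable pre-treatment and post-treatment" biopsies. Arm 4 has no biopsies.

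Section 10.B.6 (antigen spread) has a similar structure. A positive IgG response is a spot "scored by at least 3 of 4 independent reviewers" and seen in at least 2 of 3 replicates. A response to immunization is an antigen recognized at 6 months that was not recognized before treatment. No masking of any kind is stated for these reviewers.

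**The concern.** Masking should match the contrast that the reading serves. Masking the arm serves a comparison between arms. Here the reader is also asked for a comparison over time within one patient, and for that the relevant label is pre-treatment or week 12. Counting cells per field and grading PD-L1 involve judgement. A reader who could tell which slide is post-treatment, and who expects more infiltrate or more ligand, could move the later reading in that direction. The movement would look like a treatment effect in any arm with biopsies, and it would not average out as patients are added.

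At stake are the biological statements about what vaccination does in the tumor, and the analyses built on them. Exploratory objective 4 uses vaccine-induced PD-L1 as a predictor of clinical response. Exploratory objective 5 asks whether treatment elicits other regulatory molecules.

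**Working it through.** **1. Which contrasts does masking the arm protect?** Write the observed change in a patient as the true change Δ plus a reading shift b that applies to week-12 slides.

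- Between arms: (Δ₁ + b) − (Δ₂ + b) = Δ₁ − Δ₂. An equal shift cancels.
- Within patient: Δ + b. The shift stays in full.

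**2. Which questions depend on the within-patient change?**

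- Section 6 gives pTVG-HP in all four arms, so there is no unvaccinated control. Whether immunization affects tumor PD-L1, the first purpose listed in 10.D, can be answered only before against after.
- Section 9.M places the Arm 2 week-12 biopsy before the first pembrolizumab dose. The Arm 2 change is therefore the vaccine-only estimate.
- Section 11.C describes Arm 3 as non-randomized. Its paired change has no concurrent control.
- By contrast, secondary objective 2 (effect of schedule on biopsy PD-L1) and the question about concurrent anti-PD-1 and CD8+ infiltration are largely Arm 1 against Arm 2 contrasts. The arm masking suits these.

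**3. Does specimen coding mask the time point anyway?** Section 12.A labels materials with a subject number and gives confidentiality as the reason. It allows specimens to be listed by codes for subject and time point. This neither masks the time point nor shows that the reader sees it.

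**4. Illustration of size.** The plan gives no power or error rate for the biopsy change, so there is no figure to reproduce.

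- From the documents: 6 pairs per arm (Section 9); 12 pairs for Arms 1 and 2 together (6 + 6); two-sided 0.05 as the default level (Section 11.F.1).
- Assumed: a paired t-test; true change zero; shift d of 0, 0.25 or 0.5 SD of the paired differences.
- Formula: rejection probability = P(|T| > c), where T is noncentral t with n − 1 degrees of freedom and noncentrality d√n, and c is the 97.5% point of the central t.

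| Pairs n | c | d = 0 | d = 0.25 | d = 0.5 |
|---|---|---|---|---|
| 6 | 2.571 | 5% | d√n = 0.612: 8.0% | d√n = 1.225: 17.1% |
| 12 | 2.201 | 5% | d√n = 0.866: 12.4% | d√n = 1.732: 35.3% |

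The rate rises with n because a systematic shift stays the same size while the standard error shrinks.

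**The case against.** Much of the case on the other side stands.

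- **Silence is not disclosure.** A reader might infer that the pathologist will know which slide is post-treatment. The protocol does not say so, and slides are handled by a pathology laboratory whose procedures are not shown. What can be said is that the plan specifies masking and specifies it for arm only.
- **Dated labels.** Section 15.C says stored samples "will be labeled with this unique code and the date of preparation", and one might infer that slides carry dates too. That section covers blood specimens. It also keeps the database that links codes to subjects and time points from laboratory personnel other than the investigators. It is no evidence about biopsy slides.
- **Limited reach.** The results concerned are secondary or exploratory, with about 6 pairs per arm of a pilot trial. The formal schedule comparison is largely protected.
- **The test is not in the plan.** Section 11.F names no paired test for biopsy markers. F.5.2 is descriptive for PD-L1 levels, F.6.4 uses logistic regression and F.6.5 linear regression. The percentages are therefore hypothetical. The bias itself does not depend on the test, because an estimated mean change would carry the same shift.
- **Immunoblot safeguards.** Agreement of reviewers and replicates, confirmatory ELISA where feasible, and the option of statistically defined criteria with commercial antigens all limit individual scoring error. They do not remove an expectation shared by all four reviewers. The scoring follows cited publications that cannot be checked here and may describe masking.
- **PET.** Section 10.E has the FLT PET analyst "and designees blinded to study treatment arm", and a reader might extend the point to those scans. The extension fails. All PET data are coregistered to the pre-treatment scan, so the analyst must know which scan is baseline.

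**Conclusion.** The point holds in a limited form. Section 10.D provides masking for the arm contrast but none for the within-patient change that it asks the same reader to determine. That change is the only route to the question whether immunization affects tumor PD-L1, and it feeds exploratory objectives 4 and 5. The primary endpoints (safety, progression, response) are untouched, and the Arm 1 against Arm 2 contrast is largely protected if the shift is equal in both arms.

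The size cannot be taken from the documents. With no true change, a paired two-sided 5% t-test and a shift of 0 to 0.5 SD, the false-positive rate lies between 5% and 17% for 6 pairs and between 5% and 35% for 12. The lower end applies if the time point is in fact masked or the reader is unaffected. A reader might infer that the biopsy results are biased, or that these rates will occur; the documents support neither. They support a cheap improvement that is worth making before slides are scored, because afterwards only a masked re-read could separate a real change from expectation.

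**What to change.** Add to Section 10.D: slides from both time points of a patient are coded without date, time point or arm; each patient's pair is read in random order; the code is broken only after scores are locked. The expected reading shift between time points is then zero, and the illustrative false-positive rate returns to 5%.

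Add the same coding rule to Section 10.B.6 for the membranes scored by the four reviewers. Leave Section 10.E as it is.

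The cost is one sentence in each of the two sections, plus recoding of slides and membranes. The readers and specimens stay the same and no patients are added. The one downside is that readings wait until the second specimen is available.
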